10.4 Analysis of Vital Signs and Weight

Vital sign variables include: body temperature, pulse (sitting, standing and orthostatic), diastolic blood pressure (sitting, standing and orthostatic), and systolic blood pressure (sitting, standing and orthostatic).

Weight variables include: weight and BMI.

Orthostatic variables will be calculated as the change from sitting to standing (standing measurement minus sitting measurement).

BMI will be calculated using height as measured during screening.

10.4.1 Vital Sign and Weight Mean Changes

Analyses of mean change from baseline to each planned visit and to the minimum, maximum and final value during the 12-week Treatment Period will be presented by treatment group for each vital sign and weight variable.

For each change from baseline analysis, the following summary statistics for each treatment group will be presented: sample size, baseline mean, visit (time point) mean, and the mean, standard deviation, and median of the change from baseline. The baseline and visit (time point) means will be calculated for each visit (time point) for subjects who have both a baseline and visit (time point) value. The mean changes for the LCIG group and for the OMT group will be compared using an ANOVA with treatment as the factor. LS mean, standard error, 95% confidence interval and *P* value will be presented.

Analyses of mean change from baseline to each planned visit and to the minimum, maximum and final value during the Transition Period will be presented for each vital sign and weight variable for LCIG subjects who enter the Transition Period.

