5.1 Overall Study Design and Plan: Description

This is a Phase 3b, open-label, randomized multicenter 12 week study assessing the efficacy of LCIG treatment compared to OMT on dyskinesia in subjects with Advanced Parkinson's Disease.

This study will be conducted at approximately 22 - 28 sites that specialize in movement disorders in approximately 6 - 8 countries where LCIG is commercially available.

The study will consist of 3 sequential periods: Screening, Treatment and Follow-Up. The OMT group will have the same schedule of visits/procedures throughout the study as the LCIG treatment group, except for visits related to NJ/PEG procedures, titration of LCIG and follow-up period.

Patients, who in collaboration with their physicians at participating centers have been found eligible for inclusion into this study during the screening period, will be enrolled into this study.

[figure not shown]

Figure 2. Study Design Schematic

* Follow up period only applicable to LCIG treatment arm subjects that have discontinued the study for any reason. 7 days after the PEG-J removal, a follow-up visit (V9) will be conducted.

The study is designed to enroll an adequate number of subjects such that approximately 60 subjects will be randomized in a 1:1 ratio to either treatment group of OMT or LCIG treatment in order to meet scientific and regulatory objectives without over-enrolling an undue number of subjects in alignment with ethical considerations.

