5.3 Efficacy and Safety Assessments/Variables

5.3.1 **Efficacy and Safety Measurements Assessed and Flow** Chart

After a subject has signed the Informed Consent, the study activities described in Table 4 will be completed. Subject visit days should ideally match the target clinic visit days. Every attempt should be made to bring the subject back on the target visit day. For all study visits apart from V1 to V3 a \pm 3 days visit window will be allowed. All attempts should be made to return the subject to the planned visit schedule (e.g., if the subject is 2 days late for a Study Visit, the scheduling of the next visit date should be based on the original planned visit date). All scheduled visits are calculated based on Study Day 1 (NJ and/or PEG-J Placement Day for subjects randomized to LCIG Treatment and the day after randomization for subjects randomized to OMT).

ODOVIE Levodopa-Carbidopa Intestinal Gel/Carbidopa Levodopa Enteral Suspension M15-535 Protocol Amendment 1 EudraCT 2016-001403-23

Table 4. Study Activities

		OMT/LCIG	D	LCIG Treatment	ıtment	0	MT/LC	OMT/LCIG Treatment	atment	TCIG I	LCIG Treatment
	V1	V2	V3	V4 NJ/PEG-J	Titration	V5 Wk	V6 Wk	V7 Wk	8A	64	Transition to Commercial
Activity	Screening	Screening	Randomization	Placement D1	Visits	2	4	8	Wk 12/ET	$ m Wk13FU^a$	Visits ^D
Visit Number for OMT/LCIG	V1	V2 ^c (Optional)	V3	V4 ^d		V5	9/	77	8Λ	6Λ	Every 6 and 12 Weeks
Informed Consent ^e	×										
Medical/Neurological/PD History	×		X ^f								
Concomitant Medication (including anti-PD and Dyskinesia medications)	×	×	X	X	X	×	×	×	X	X	X
Anti-PD Medication History	×										
Physical Examination ^g	×	×	X	X		×	×	×	X	X	
Neurological Exam	X	X	X			X	X	X	X	X	
Dermatological Exam ^g	X								X		
GI Exam ^g	X								X		
NJ or PEG-J decision	X										
Nasojejunal Tube Placement/Titration (Optional)				X							
PEG-J Placement Procedure				X							

ODOVIE Levodopa-Carbidopa Intestinal Gel∕Carbidopa Levodopa Enteral Suspension M15-535 Protocol Amendment 1 EudraCT 2016-001403-23

Table 4. Study Activities (Continued)

		OMT/LCIG	S)	LCIG Treatment	ıtment	0	MT/LC	OMT/LCIG Treatment	ıtment	LCIG 1	LCIG Treatment
						VS	9/	V7			Transition to
Activity	V1 Screening	V2 Screening	V3 Randomization	V4 NJ/PEG-J Placement D1	Titration Visits	2 Wk	≱ 4	× ××	V8 Wk 12/ET	V9 Wk 13 FU ^a	Commercial Visits ^b
Radiological Check of Tube Placement				X							
PEG-J Site (Stoma) Check				X^{j}	×					×	
Vital Signs/Weight	X		X	X	×	×	×	×	X	×	X
Height	X										

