8.1.4.4 Vital Sign Variables and Weight

For each vital sign and weight variable, analyses of the mean change from baseline to each scheduled visit and to the final value will be presented by treatment group and for both treatment groups combined. For this analysis, the average of multiple observations on the same day will be calculated and treated as the observation for the day.

Criteria for potentially clinically significant (PCS) values for selected vital sign and weight variables will be pre-specified in an SAP prior to database lock. For each variable, a summary of the number and percentage of subjects who have at least one post-baseline observation that meets the PCS criteria and is more extreme than their baseline value will be provided.

8.1.4.5 **ECG Variables**

For each ECG variable, analyses of the mean change from baseline to each scheduled visit and to the final value will be presented by treatment group and for both treatment groups combined. For this analysis, the average of multiple observations on the same day will be calculated and treated as the observation for the day.

Criteria for potentially clinically significant (PCS) values for selected ECG variables will be pre-specified in an SAP prior to database lock. For each variable, a summary of the number and percentage of subjects who have at least one post-baseline observation that meets the PCS criteria and is more extreme than their baseline value will be provided for each treatment group and for both treatment groups combined.

8.1.4.6 **Additional Safety Variables**

The following additional summaries of safety measures will be prepared.

- The number of subjects with 1 or more positive screens on a Minnesota Impulsive Disorders Interview (MIDI) module at baseline as well as during the treatment period, and
- The number of subjects with 1 or more affirmative responses to the Columbia Suicide Severity Rating Scale (C-SSRS) at baseline as well as during the treatment period.

8.1.5 **Interim Analysis**

No interim analysis is planned for this study.

8.2 **Determination of Sample Size**

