6.5 Analysis by Planned Visit for Non-Diary Variables

A midpoint convention will be used to assign all observations to a planned visit based on the Study Day of the observation. If there are multiple observations on the same day, the average will be taken and considered the observation for the day. If more than one observation is assigned to a planned visit, the last observation will be selected and considered the observation for the planned visit.

The following Study Day windows will be used to assign efficacy and health outcome assessments to planned study visits during the 12-week Treatment Period. Assessments

on the day of first day of LCIG infusion via PEG-J are not planned and will not be included in the analysis.

Assessment	Planned Visit	Nominal Study Day	Study Day Range ^a
UDysRS, UPDRS,	Baseline		\leq date of randomization
mAIMS, CGI-C	Week 2	14	2 - 21
	Week 4	28	22 - 42
	Week 8	56	43 - 70
	Week 12	84	≥ 71
PDQ-8	Baseline		\leq date of randomization
	Week 8	56	2 - 70
	Week 12	84	≥ 71
King's PD Pain Scale	Baseline		\leq date of randomization
	Week 4	28	2 - 42
	Week 8	56	43 - 70
	Week 12	84	≥ 71

a. For subjects in LCIG group, all post-baseline assessments must also be after start of LCIG infusion through PEG-J and no more than 1 day after the date of the last LCIG infusion in the 12-week Treatment Period.

The following Study Day windows will be used to assign safety assessments during the
12-week Treatment Period to planned study visits.

Assessment	Planned Visit	Nominal Study Day	Study Day Range ^a
Vital signs and weight,	Baseline		\leq date of randomization
MIDI, Sleep Attacks	Week 2	14	2 - 21
Questionnaire, C-SSRS	Week 4	28	22 - 42
	Week 8	56	43 - 70
	Week 12	84	≥ 71
	Week 13 FU ^b	91	$2 \leq RxEnd Days$
Clinical labs and	Baseline		\leq date of randomization
Electrocardiograms, Special labs	Week 8	56	1 - 70
Special laus	Week 12	84	≥ 71

For subjects in LCIG group, all post-baseline assessments must also be no more than 1 day after the final PEG-J a. removal for subjects who do not transit to commercial product or no more than 1 day after the final Study M15-535 LCIG infusion during 12-week Treatment Period for subjects who transit to commercial product.

b. Applicable only to LCIG subjects who will not continue on commercial product.

For LCIG subjects who enter the Transition Period, vital signs and weight, special labs, C-SSRS and MIDI will be assessed every 12 weeks.

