10.4.3 Potentially Clinically Significant (PCS) Vital Sign and Weight Values

Criteria for PCS values have been predefined for selected vital sign and weight variables as outlined in Appendix B. For each variable, a summary of the number and percentage of subjects in each treatment group who have at least one post-baseline observation during the 12-week Treatment Period that meets the PCS criteria and is more extreme than their baseline value will be provided.

A summary of the number and percentage of subjects who have at least one observation during the Transition Period that meets the PCS criteria and is more extreme than their baseline value will be provided for LCIG subjects who enter the Transition Period.

A listing will also be prepared that will include, for each variable, all observations for each subject that met the PCS criteria for that variable at any time during the study. No comparisons of treatment groups will be performed.

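### SAP 10.4.1 tests LCIG against OMT on each subject's lowest and highest vital sign and weight, although LCIG subjects have extra readings at V4 and titration visits

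*SAP*

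**What the plan says.** **Tests.** For every vital sign and weight variable, SAP 10.4.1 calls for "Analyses of mean change from baseline to each planned visit and to the minimum, maximum and final value during the 12-week Treatment Period", and adds: "The mean changes for the LCIG group and for the OMT group will be compared using an ANOVA with treatment as the factor". An LS mean, standard error, 95% confidence interval and P value follow. SAP 10.1 sets safety tests at two-sided 0.050.

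**Schedule.** The visit schedules of the two arms match "except for visits related to NJ/PEG procedures, titration of LCIG and follow-up period" (Protocol 5.1). In the row "Vital Signs/Weight" of Protocol Table 4, repeated in SAP Appendix A, both arms are marked at V5 to V8 (Weeks 2, 4, 8 and 12). V4 and the titration visits are marked as well, and these belong to LCIG only. Protocol 5.1.2.1 gives OMT no V4. Protocol 5.1.2.2 lets titration visits happen as needed, so their number is not fixed.

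**Which readings count.** SAP 6.5, headed as the analysis by planned visit, states: "If more than one observation is assigned to a planned visit, the last observation will be selected". Its vital sign windows open on Study Day 2. The SAP does not say whether a period minimum or maximum is limited to these windowed values.

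**PCS values.** SAP 10.4.3 reports by arm the subjects "who have at least one post-baseline observation during the 12-week Treatment Period that meets the PCS criteria", and closes with "No comparisons of treatment groups will be performed".

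**Protocol.** Protocol 8.1.4.4 plans for vital signs and weight only that "analyses of the mean change from baseline to each scheduled visit and to the final value will be presented by treatment group". Minimum and maximum analyses are planned for laboratory variables (8.1.4.3). SAP 12.0 declares no change in analysis from the protocol.

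**The concern.** The largest of several noisy readings rises on average with the number of readings, and the smallest falls. If one arm is read four times and the other five to ten times, the arms differ in expected maximum and minimum even when treatment does nothing. An ANOVA on those extremes then tests the measurement schedule as well as the drug and does not hold its 5% level.

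This bears on two safety topics the protocol singles out: orthostatic hypotension is an identified risk (Protocol 3.2) and weight loss is an adverse event of special interest (Protocol 6.2.3). A small P value for lowest blood pressure or lowest weight would be read as a treatment effect when part or all of it could come from more frequent measurement during titration.

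**Working it through.** The documents give no figure for these analyses, so there is none to reproduce.

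**Inputs from the documents**
- About 60 subjects randomized 1:1 (SAP 4.3), so 30 per arm.
- OMT: 4 post-baseline readings (Weeks 2, 4, 8, 12).
- LCIG: the same 4 plus *m*, where *m* counts V4 and titration readings together. The documents do not fix *m*.

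**Assumptions**
- *m* = 0, 1, 2, 4 or 6.
- Normal within-subject noise with SD 1, one baseline reading and no treatment effect.

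**Step 1: expected maximum of *k* independent readings, in SD units**
- *k* = 4: 1.029; *k* = 5: 1.165; *k* = 6: 1.267; *k* = 8: 1.423; *k* = 10: 1.541.
- Excess over *k* = 4: 1.165 − 1.029 = 0.136; 1.267 − 1.029 = 0.238; 1.423 − 1.029 = 0.394; 1.541 − 1.029 = 0.512.
- The minimum is the mirror image.

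**Step 2: rejection rate.** I simulated null trials with 30 per arm, 8,000 per setting. The test was the two-group ANOVA on change from baseline to the extreme, which for two arms is a t test.

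| Extra LCIG readings | Null shift (SD) | Rejection at nominal 5% |
|---|---|---|
| 0 | 0 | about 5% |
| 1 | about 0.13 | about 7% |
| 2 | about 0.24 | about 12% |
| 4 | about 0.40 | about 24% |
| 6 | about 0.51 | about 37% |

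**Step 3: correlated readings.** Titration readings lie days apart, so independence is an upper-end assumption for slowly changing variables.
- Correlation decaying exponentially over about 7 days: rejection about 9% to 16% for 2 to 6 extra readings.
- Slower decay, over 30 to 90 days, closer to what one would expect for weight: shift about 0.10 to 0.19 SD and rejection about 8% to 11%.
- The form of the correlation matters. A fixed 0.5 between successive readings, whatever their spacing, gives 14%, 30% and 47% for 2, 4 and 6 extra readings. That ignores the crowding of titration readings, so I put less weight on it.

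**Step 4: PCS percentages (not tested).** With an assumed, independent chance *p* = 2% per reading, the chance of at least one PCS value is 1 − (1 − *p*)^*k*:
- 4 readings: 1 − 0.98^4 = 7.8%.
- 6 readings: 1 − 0.98^6 = 11.4%.
- 10 readings: 1 − 0.98^10 = 18.3%.

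Independence is not credible for weight, where SAP Appendix C defines a PCS value as a change of at least 7% from baseline.

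**Step 5: after the fix.** With the four common visits in both arms, the expected null shift is 0 and simulated rejection is 4.8% to 5.4%.

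**The case against.** The strongest objection is that SAP 6.5 may already equalise the arms. It assigns all observations to planned visits and keeps one per window. If the minimum and maximum are taken over those retained values, each arm contributes four and the artefact vanishes. The Day 2 start of the vital sign windows would also leave out a V4 reading on Day 1. This reading is possible. It is less natural, because 6.5 is headed as planned-visit analysis, 10.4.1 lists minimum and maximum separately from planned visits, and nothing excludes a post-baseline reading outside the windows from a period extreme. At best the SAP is silent, and two programmers could produce different tables.

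The second objection is size, and it stands. Titration may be done in hospital with few clinic visits afterwards, so zero or one extra reading is plausible. Rejection is then about 5% to 7%. The 37% figure needs six extra independent readings.

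Three stronger inferences are tempting, and the documents do not support them:
- *The SAP tests the arms on PCS values.* SAP 10.4.3 rules out treatment-group comparisons, so only side-by-side percentages are affected.
- *All P values in 10.4.1 are wrong.* The last-in-window rule gives one value per subject for each planned visit, and the mechanism does not act on a single final value. V9 does not add to the imbalance either: it falls a week after PEG-J removal, and the SAP's limit is 1 day after.
- *Laboratory extremes share the problem.* Scheduled laboratory samples are the same in both arms during treatment, and the panel triggered by polyneuropathy symptoms is not specific to one arm.

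These are also safety tests outside the efficacy gatekeeping, so no efficacy claim depends on them.

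**Conclusion.** The concern holds for the tested minimum and maximum of vital signs and weight, on the condition that all treatment-period readings are used. On that reading the direction is certain: LCIG maxima are pushed up and minima down with no drug effect. The size is not certain. Rejection of a true null is about 7% with one extra reading. It is about 9% to 16% with two to six extra readings correlated over about 7 days, and about 12% to 37% if those readings are independent. These figures rest on 30 per arm, four OMT readings, and an assumed number and correlation of extra readings. Weight probably lies near the low end.

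For PCS values the point is only that the percentages set side by side rest on unequal numbers of readings.

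Separately, and whichever way SAP 6.5 is read, the minimum and maximum analyses of vital signs and weight are additions to the protocol that SAP 12.0 does not record. The SAP should be changed before the analysis is run.

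**What to change.** - **SAP 10.4.1:** compute the tested minimum and maximum in both arms from the Week 2, 4, 8 and 12 planned-visit values only, or drop those tests. Summarise V4 and titration readings for LCIG separately.
- **SAP 10.4.3:** keep all observations, and either footnote that the arms have unequal numbers of readings or add a by-arm row restricted to the common visits. Moving titration PCS values out of the table altogether is less attractive, because it removes readings taken around tube placement and titration from the by-arm safety percentages.
- **SAP 12.0:** if the minimum and maximum analyses stay, record them as an addition to Protocol 8.1.4.4.

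The cost is a few sentences and one programming flag. The downside is that LCIG titration-period extremes leave the tested comparison, but they remain reported in the separate summary, and no data are lost.

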10.4.2 Shifts in BMI Category

BMI values will be categorized as low (< 18.5 kg/m²), normal (18.5 kg/m² to < 25 kg/m²), overweight (25 kg/m² to < 30 kg/m²) or obese (\geq 30 kg/m²). Shift tables will be prepared summarizing BMI category shifts from baseline to lowest, highest and final value during the 12-week Treatment Period for each treatment group. No comparisons of treatment groups will be performed.

10.4.3 Potentially Clinically Significant (PCS) Vital Sign and Weight Values

Criteria for PCS values have been predefined for selected vital sign and weight variables as outlined in Appendix B. For each variable, a summary of the number and percentage of subjects in each treatment group who have at least one post-baseline observation during the 12-week Treatment Period that meets the PCS criteria and is more extreme than their baseline value will be provided.

A summary of the number and percentage of subjects who have at least one observation during the Transition Period that meets the PCS criteria and is more extreme than their baseline value will be provided for LCIG subjects who enter the Transition Period.

A listing will also be prepared that will include, for each variable, all observations for each subject that met the PCS criteria for that variable at any time during the study. No comparisons of treatment groups will be performed.

10.5 Analysis of Electrocardiogram (ECG) Variables

Electrocardiogram (ECG) variables include: heart rate (HR), PR interval, QRS interval, uncorrected QT interval, QT interval corrected for heart rate using Bazett's formula (QTcB) and QT interval corrected for heart rate using Fridericia's formula (QTcF).

QTcB and QTcF will be calculated for each uncorrected QT interval based on the following formulas:

- Bazett's correction (QTcB): $QT_cB = QT/\sqrt{(60/HR)}$
- Fridericia's correction (QTcF): $QT_cF = QT/\sqrt[3]{(60/HR)}$

10.5.1 **ECG Mean Changes**

Analyses of mean change from baseline to each planned visit and to the minimum, maximum and final value during the 12-week Treatment Period will be presented by treatment group for each ECG variable.

For each change from baseline analysis, the following summary statistics for each treatment group will be presented: sample size, baseline mean, visit mean, and the mean, standard deviation, and median of the change from baseline. The baseline and visit means will be calculated for each visit for subjects who have both a baseline and visit value. The mean changes for the LCIG group and for the OMT group will be compared using an ANOVA with treatment as the factor. LS mean, standard error, 95% confidence interval and *P* value will be presented.

10.5.2 Potentially Clinically Significant (PCS) ECG Values

Criteria for PCS values have been predefined for selected ECG variables as outlined in Appendix D. For each variable, a summary of the number and percentage of subjects in each treatment group who have at least one post-baseline observation during the 12-week Treatment Period that meets the PCS criteria and is more extreme than their baseline value will be provided. A listing will also be prepared that will include, for each variable, all observations for each subject that met the PCS criteria for that variable at any time during the study. No comparisons of treatment groups will be performed.

10.6 Analysis of Sleep Attack Questions

At Screening Visit 1, the sleep attack questions will collect history during the previous 3 months. At all other visits, the sleep attack questions will collect experience since the last visit. Affirmative responses to the sleep attack questions will be summarized by treatment for the study period on or before the date of randomization and for the study period on or after Day 1.

Each summary will include the number and percentage of subjects in each treatment group reporting a) 1 or more sleep attacks at any visit, b) 1 or more sleep attacks at any visit without sleepiness or drowsiness prior to sleep attack, and c) 1 or more sleep attacks at any visit with bad outcome during the 12-week Treatment Period. The highest number of sleep attacks reported at any visit (1, 2, 3, more than 3) will also be summarized by the number and percentage of subjects in each treatment group with each count.

A listing will also be prepared that includes all subjects who reported 1 or more sleep attacks at any visit.

